### Unscheduled visits

In general, by-visit summaries will be presented by the scheduled visits (visit number and corresponding visit name of planned clinical encounter). Visit windowing will not be used for handling unscheduled visits. Instead, all unscheduled visits will be assigned a visit name of "Unscheduled". Such visits will be included in data listings and will contribute to the derivation of best- or worst-case values where required. Data from all assessments (scheduled and unscheduled), including multiple assessments, will be listed.

## 2.2 Analysis sets

### Withdrawal of Informed Consent

Any data collected in the clinical database after a participant withdraws informed consent from all further participation in the trial, will not be included in the analysis. The date on which a participant withdraws full consent is recorded in the eCRF.

### Full Analysis Set

The full analysis set (FAS) includes all participants who received at least one dose of Lutathera.

## **Safety Set**

The safety set in this case is identical to the full analysis set.

### **Dosimetry analysis set**

The dosimetry analysis set (DAS) consists of all patients who have at least one valid (i.e. not flagged for exclusion by the dosimetrist) dosimetry measurement. The DAS will be used for summaries (tables and figures) and listings of dosimetry data and modeling.

### **PK analysis set**

The PK analysis set (PKAS) consists of all patients who have at least one valid (i.e. not flagged for exclusion) PK measurement. The PKAS will be used for summaries (tables and figures) and listings of PK data and modeling.

## **2.3 Patient disposition, demographics and other baseline characteristics**

The Full Analysis Set (FAS) will be used for all baseline and demographic summaries and listings unless otherwise specified. Summaries will be reported by cancer type (i.e. separately for GEP-NET and PPGL patients) and all patients together. No inferential statistics will be provided.

### **Basic demographic and background data**

All demographic and baseline disease characteristics data will be summarized and listed by cancer type. Categorical data (e.g. gender, ethnicity and race) will be summarized by frequency counts and percentages; the number and percentage of patients with missing data will be provided. Continuous data (e.g. age, weight, height and body mass index) will be summarized by descriptive statistics (N, mean, median, standard deviation, minimum and maximum).

### **Diagnosis and extent of cancer**

Summary statistics will be tabulated for diagnosis and extent of cancer. This analysis will include the following (when applicable for a specific cancer type): type of PPGL cancer (pheochromocytoma or paraganglioma), primary site of cancer, histological grade of GEP-NET (according to Ki-67 index), disease stage, tumor status for GEP-NET (functional vs non-functional), TNM criteria, presence of metastases, metastatic sites, primary origin, catecholamine secretion, chromaffin tissue, 123I-MIBG uptake, tumor category (non-hereditary, hereditary, unknown), time since initial diagnosis of primary disease, time since most recent relapse/progression, type of somastotatin receptor imaging and tumor uptake score.

### **Medical history**

Medical history and ongoing conditions, including cancer-related conditions and symptoms entered on eCRF will be summarized and listed by cancer type. Medical history and current medical conditions will be coded using the Medical Dictionary for Regulatory Activities

(MedDRA) terminology. The MedDRA version used for reporting will be specified in the CSR and as a footnote in the applicable tables/listings.

### **Other**

All data collected at baseline will be listed.

#### **2.3.1 Patient disposition**

The number (%) of participants included in the FAS will be presented overall and by cancer type. The number (%) of screened and not-treated participants and the reasons for screening failure will also be displayed. The number (%) of participants who discontinued the study phases and the reason for discontinuation will also be presented.

### **Protocol deviations**

The number (%) of participants in the FAS with any protocol deviation will be tabulated by deviation category (as specified in the study Data Handling Plan) overall and by cancer type.

All protocol deviations will be listed.

### **Analysis sets**

The number (%) of patients in each analysis set (defined in Section 2.2) will be summarized by cancer type.

#### **2.4 Treatments (study treatment, rescue medication, concomitant therapies, compliance)**

The Safety Set will be used for all treatment summaries and listings unless otherwise specified. Summaries will be reported by cancer type (i.e. separately for GEP-NET and PPGL patients) and all patients together. No inferential statistics will be provided.

##### **2.4.1 Study treatment / compliance**

#### **Cumulative dose**

Cumulative dose of study treatment is defined as the total dose given during the study treatment exposure and will be summarized by cancer type.

The **planned cumulative dose** for a study treatment component refers to the total planned dose as per the protocol up to the last date of investigational drug administration.

The **actual cumulative dose** refers to the total actual dose administered, over the duration for which the subject is on the study treatment as documented in the Dose Administration eCRF.

#### **Duration of exposure**

The duration of exposure in weeks is defined as (date of last administration of study treatment – date of first administration of study treatment + 8\*7) / 7.

### **Dose intensity and relative dose intensity**

**Dose intensity (DI)** for participants with non-zero duration of exposure is defined as follows:

DI (MBq / week) = Actual Cumulative dose (MBq) / Duration of exposure to study treatment (weeks).

**Planned dose intensity (PDI)** is defined as follows:

PDI (MBq / week) = Planned Cumulative dose (MBq) / Duration of exposure (weeks).

**Relative dose intensity (RDI)** is defined as follows:

RDI = DI (MBq / week) / PDI (MBq / week).

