#### 6.1.1 Investigational drug

The investigational drug Lutathera® (lutetium Lu 177 dotatate/ lutetium ( $^{177}\text{Lu}$ ) oxodotreotide) will be provided by the Sponsor ([Table 6-1](#)). Patients will receive a total of 4 administrations of Lutathera 7.4 GBq / 200 mCi every 8  $\pm 1$  weeks.

**Table 6-1** Investigational drug

| Investigational/
Control Drug
(Name and
Strength) | Pharmaceutical Dosage
Form   | Route of
Administration | Supply type          | Supplier |
|--|---|----------------------------|----------------------|----------|
| Lutathera®   | Radiopharmaceutical solution
for infusion (7.4 GBq of
Lutathera per 30 ml vial) | Intravenous use            | Open label;
vials | Sponsor  |

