|                       |                  | 12. Blood collection for dosimetry includes 6 radioactive blood samples at the following time points: before the start of Lutathera infusion, at the end of Lutathera infusion, then at 2h, 6h, 24h and 72h after the end of Lutathera infusion.
13. On Day 1 of Cycle 1, safety biomarkers are assessed pre-dose.
14. Safety biomarkers are taken either at Week 7 of cycle 1 or pre-dose of cycle 2.
15. Safety Biomarkers are taken either at Week 7 of cycle 4 or at the EoT visit.
S = assessment to be recorded in the source documentation only and not recorded in CRF page.
* The last FU visit would be the EOS visit for patients who completed the long-term FU period; and a separate EOS visit should be planned for patients who discontinued from the study prior to completion of the long-term FU period. |                |               |         |               |         |         |            |         |         |  |                          |                          |                          |  |

Variations of  $\pm$  1 week are allowed for the visits during the Treatment period (including the window for Lutathera administration visits that should occur in 8 weeks from the previous dose  $\pm$  1 week), and during the Short-term Follow-up. The exception is the week when dosimetry assessments are performed – during the dosimetry week, all visits must occur on the Days specified in the [Table 8-2](#).

During the Long-term Follow-up, a visit window of  $\pm$  1 month is allowed.

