## **12.3 Treatments**

The FAS will be used for the analyses below.

The cumulative dose (MBq) will be summarized by means of descriptive statistics. The number of subjects who have dose reductions, permanent discontinuations or interruptions, and the reasons will also be summarized.

Concomitant medications and significant non-drug therapies prior to and after the start of the study treatment will be listed and summarized according to the Anatomical Therapeutic Chemical (ATC) classification system for all participants.

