### **Dose reductions, interruptions or permanent discontinuations**

The number of subjects who have dose reductions, permanent discontinuations or interruptions, and the reasons, will be summarized.

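### Relative dose intensity divides both planned and actual dose by the patient's own exposure time, so it cannot show delay in a patient who receives all four doses

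*SAP*

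**What the plan says.** The definitions are all in SAP 2.4.1.

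- **Duration of exposure:** "The duration of exposure in weeks is defined as (date of last administration of study treatment", minus the first administration date, plus 8 × 7 days), divided by 7. Both dates are the patient's actual dates.
- **Dose intensity (DI):** "DI (MBq / week) = Actual Cumulative dose (MBq) / Duration of exposure to study treatment (weeks").
- **Planned dose intensity (PDI):** "PDI (MBq / week) = Planned Cumulative dose (MBq) / Duration of exposure (weeks").
- **RDI:** DI divided by PDI.
- **Planned cumulative dose:** it "refers to the total planned dose as per the protocol up to the last date of investigational drug administration".

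The SAP gives no separate planned duration, and its section 4 reports no change to protocol-specified analyses.

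For reporting, SAP 2.4.1 commits to the cumulative dose and states: "The number of subjects who have dose reductions, permanent discontinuations or interruptions, and the reasons, will be summarized". Protocol 12.3 says: "The cumulative dose (MBq) will be summarized by means of descriptive statistics". The regimen is in Protocol 6.1.1: "Patients will receive a total of 4 administrations of Lutathera 7.4 GBq / 200 mCi every 8" ± 1 weeks.

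**The concern.** A relative dose intensity should compare the rate at which drug was given with the rate that was planned. Here the patient's own delay enters the planned rate as well as the actual one, so the two always move together. The SAP would assign a delayed patient a planned intensity that the protocol never plans.

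Protocol 6.5.1.1 foresees such delays. It allows the interval to be extended from 8 to 16 weeks for severe or intolerable reactions, and it calls for temporary discontinuation for intercurrent disease and around major surgery. At stake is one descriptive exposure statistic: an RDI of 100% would be read as treatment delivered at the planned intensity when it says only that the planned amount was given. With as few as 8 patients, one delayed patient changes the summary. If seven patients are at 100% and one at 80.0%, the mean is (7 × 100 + 80)/8 = 97.5% and the minimum 80.0%, where the SAP formula would show 100% for both.

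**Working it through.** **Inputs**

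- Regimen: 4 × 7,400 MBq every 8 weeks (Protocol 3 and 6.1.1).
- Duration D = (last date − first date + 56 days)/7 (SAP 2.4.1).
- Interval extension up to 16 weeks; resumption at 3,700 MBq after a dose-modifying toxicity; 12-week wait after major surgery (Protocol 6.5.1.1 and Table 6-4).
- Visit window ± 1 week (text after Protocol Table 8-2); per-dose tolerance ± 10% (Protocol 6.6.1).

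**The plan's own figure.** 4 × 7.4 GBq = 29.6 GBq, as stated. The documents print no DI, PDI or RDI value.

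**Algebra.** With actual dose A and planned dose P, RDI = (A/D)/(P/D) = A/P. D drops out.

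**Planned rate.** D = 24 + 8 = 32 weeks; 29,600/32 = 925 MBq/week.

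**Patients who receive four doses**

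| Pattern | A (MBq) | D (weeks) | DI (MBq/week) | RDI as written | DI/925 |
|---|---|---|---|---|---|
| On schedule | 29,600 | 32 | 925 | 100% | 100% |
| One 16-week interval | 29,600 | 40 | 740 | 100% | 80.0% |
| Two 16-week intervals | 29,600 | 48 | 616.7 | 100% | 66.7% |
| Three 16-week intervals | 29,600 | 56 | 528.6 | 100% | 57.1% |
| One 16-week interval, one dose halved | 25,900 | 40 | 647.5 | 87.5% | 70.0% |

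In the last row, A = 3 × 7,400 + 3,700, and the 87.5% reflects the halved dose only. The position of the long interval does not matter.

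**How four full doses and a long interval can arise.** The surgery provision states a delay without a dose reduction. The timing of surgery is not given and is an assumption here. If surgery falls s weeks after a dose, the interval is s + 12 weeks, D = 24 + s + 12, and DI/925 = 32/(36 + s):

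- s = 0: 32/36 = 88.9%
- s = 4: 32/40 = 80.0%
- s = 8: 32/44 = 72.7%

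RDI as written is 100% in each case.

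**Does the wording of planned cumulative dose rescue the formula?** The phrase about the last date can mean 7,400 MBq per administration given, or per 8-week calendar slot reached by that date. In every row of the table both readings give P = 29,600, because the regimen stops at four doses. The readings differ only when dosing departs from the nominal 8-week slots:

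| Full doses given | By administrations | By calendar slots |
|---|---|---|
| Two, 16 weeks apart, then stop | 14,800/14,800 = 100% | 14,800/22,200 = 66.7% |
| Three, one 16-week interval, then stop | 22,200/22,200 = 100% | 22,200/29,600 = 75.0% |
| Two, 7 weeks apart, then stop | 14,800/14,800 = 100% | 14,800/7,400 = 200% |
| Four, every 7 weeks | 29,600/29,600 = 100% | 29,600/22,200 = 133.3% |

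The last two patterns lie inside the permitted visit window.

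**Effect of a fixed 925 MBq/week on compliant patients**

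- Three 7-week intervals: D = 29; 29,600/29 = 1,020.7; 110.3%.
- Three 9-week intervals: D = 35; 29,600/35 = 845.7; 91.4%.
- Adding the dose tolerance: 32,560/29 = 1,122.8, or 121.4%; 26,640/35 = 761.1, or 82.3%.
- The present ratio, counted by administrations, would span 90% to 110%.

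**The case against.** The strongest reply is that this is a matter of naming with no practical effect. The SAP defines RDI explicitly, and the definition can be applied without error. The visible text commits to summaries of cumulative dose and of reductions, interruptions and discontinuations, and nowhere to a table of RDI. No endpoint or dosing decision uses it. Delay shows elsewhere: in the main example duration rises from 32 to 40 weeks and DI falls from 925 to 740 MBq/week. All of this stands, and it limits the weight of the point. It does not make the formula right: a quantity in MBq/week labelled as planned takes the value 740 when the plan is 925.

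A second reply is that the 100% versus 80.0% contrast is the starkest case. Table 6-4 pairs withholding for toxicity with resumption at the reduced dose, and on that path the present RDI is 87.5%. This is fair. Four full doses with a 16-week interval need another cause of delay, such as surgery at an assumed time. On the toxicity path the delay is still invisible, since the 87.5% comes entirely from the halved dose.

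A third reply is that a fixed planned rate has faults of its own. It spreads compliant patients over 91.4% to 110.3%. It also misses a dose that is withheld and never resumed, because duration ends 8 weeks after the last dose given: two full doses on schedule followed by a hold and permanent discontinuation remain at 100%. Both are true, and they make relabelling a reasonable alternative.

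**Conclusion.** The point holds, and it is minor. As written, RDI equals actual over planned cumulative dose and carries no information on timing for any patient who receives all four doses. For one 16-week interval the gap is 100% versus 80.0% with full doses, and 87.5% versus 70.0% with one dose halved. These figures rest on the SAP's formulas and the protocol regimen, and hold on either reading of planned cumulative dose. The only assumption is how four full doses come to have such an interval. The ambiguity in planned cumulative dose is a separate and smaller matter. The consequence is confined to the descriptive exposure section, and arises only if RDI is reported.

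**What to change.** Make one of two changes in SAP 2.4.1.

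1. **Correct the formula.** Define PDI as planned cumulative dose over planned duration for the same number n of administrations: n × 7,400 MBq/(n × 8 weeks) = 925 MBq/week for every n. Keep RDI as DI over PDI. Add a footnote that dosing within the visit window alone moves RDI between about 91.4% and 110.3%, and that a hold ending in permanent discontinuation does not count as delay. The reading of planned cumulative dose then no longer affects RDI.
2. **Correct the label.** Keep the ratio and call it relative cumulative dose. This leaves compliant patients near 100% on the count of administrations, but the SAP must then say whether planned cumulative dose counts administrations given or calendar slots reached. The same statement is needed if planned cumulative dose is reported under option 1.

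The cost is one formula or one label, a footnote, and an edit to the exposure program if RDI is tabulated. No new data are needed, and no endpoint or dosing rule changes.

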### **Dose reductions, interruptions or permanent discontinuations**

The number of subjects who have dose reductions, permanent discontinuations or interruptions, and the reasons, will be summarized.

## **2.4.2 Prior, concomitant and post therapies**

### **Prior anti-cancer therapy**

Prior anti-cancer therapies are those therapies that started before the study treatment irrespective of when it ended. A therapy starting prior to the start of study treatment and continuing after the start of study treatment will be considered as both prior and concomitant.

The number and percentage of participants who received any prior anti-neoplastic medications, prior anti-neoplastic radiotherapy or prior anti-neoplastic surgery will be summarized by cancer type. Prior anti-neoplastic medications will be summarized by setting (e.g. adjuvant, metastatic, etc.) and also by lowest Anatomical Therapeutic Chemical (ATC) class and preferred term (PT).

Separate listings will be produced for prior anti-neoplastic medications, radiotherapy, and surgery.

Anti-neoplastic medications will be coded using the World Health Organization Drug Dictionary (WHO-DD); anti-neoplastic surgery will be coded using MedDRA. Details regarding MedDRA and WHO-DD version will be included in the footnote in the tables/listings.

The above analyses will be performed using the FAS.

### **Post treatment anti-cancer therapy**

Anti-neoplastic therapies since discontinuation of study treatment will be listed and summarized by ATC class, preferred term by means of frequency counts and percentages using FAS.

### **Concomitant medications**

Concomitant therapy is defined as all interventions (therapeutic treatments and procedures) other than the study treatment administered to a patient coinciding with the study treatment period. Concomitant therapy include medications (other than study drugs) starting on or after

the date of first administration of study treatment or medications starting prior to the start date of study treatment and continuing after the start date of study treatment.

Concomitant medications will be coded using the WHO-DD and summarized by lowest ATC class and PT using frequency counts and percentages. Surgical and medical procedures will be coded using MedDRA and summarized by System Organ Class (SOC) and PT. These summaries will include:

1. Medications starting on or after the date of first administration of study treatment but no later than 56 days after the date of last administration of study treatment and
2. Medications starting prior to the date of first administration of study treatment and continuing after the date of first administration of study treatment.

All concomitant therapies will be listed. Any concomitant therapies starting and ending prior to the date of first administration of study treatment or starting more than 56 days after the date of last administration of study treatment will be flagged in the listing. The safety set will be used for all concomitant medication tables and listings.

## 2.5 Analysis of the primary objective

The primary objectives of the study are to evaluate organ radiation doses as well as safety and tolerability of Lutathera in adolescent patients with SSTR-positive GEP-NETs and PPGLs as a pooled cohort. Summaries will be reported by cancer type (i.e. separately for GEP-NET and PPGL patients) and all patients together.

### 2.5.1 Primary endpoint

#### Dosimetry

The primary endpoint of the study will be the target organ (e.g. kidney and bone marrow) absorbed radiation doses in adolescents with SSTR-positive GEP-NETs and PPGLs as a pooled cohort.

#### Safety

Adverse events and laboratory toxicities occurring during the first cycle of the GEP-NET and PPGLs as a pooled cohort are also considered as primary endpoints.

### 2.5.2 Statistical hypothesis, model, and method of analysis

No statistical hypothesis will be tested in the context of this descriptive study.

#### Dosimetry

The analysis of dosimetry primary endpoint will consist of descriptive summaries and graphical presentations of the absorbed radiation doses in the target organs (e.g. kidney, bone marrow).

Whole body planar, SPECT/CT imaging, blood and urine radioactivity data (measured by gamma-counter) will be used by the dosimetry vendor to calculate the absorbed radiation dose in the target organs.

The details of the dosimetry parameters derivations are given in the Imaging, Dosimetry and Pharmacokinetics Manual.

## Safety

Adverse events and laboratory toxicities occurring during the first cycle will be summarized descriptively to evaluate the acute toxicities induced by a single full-dose Lutathera infusion (7.4 GBq).

The following AE summaries will be produced based on the safety set for the first cycle of treatment:

- AEs regardless of study drug relationship by SOC, PT, and severity.
- AEs suspected to be study drug related by SOC, PT, and severity;
- SAEs regardless of study drug relationship by SOC, PT, and severity.
- SAEs suspected to be study drug related by SOC, PT, and severity;

The following summaries will be produced for hematology and biochemistry laboratory data (by laboratory parameter):

- Worst post-baseline CTC grade (regardless of the baseline status). Each participant will be counted only for the worst grade observed during the first cycle post-baseline.
- Shift tables using CTC grades to compare baseline to the worst on-treatment value observed during the first cycle.
- For laboratory tests where CTC grades are not defined, shift tables using the low/normal/high/(low and high) classification to compare baseline to the worst on-treatment value observed during the first cycle.

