**Table 6-4 Recommended Dose Modifications of Lutathera for Adverse Events**

| Adverse Reaction | Worst Toxicity CTCAE Grade (unless otherwise specified)   | Dose Modification  |
|------------------|---|--|
| Thrombocytopenia | First occurrence of:
Grade 2 (PLT < 75 - 50 x 10  /L)
Grade 3 (PLT < 50 - 25 x 10  /L)
Grade 4 (PLT < 25 x 10  /L) | Withhold dose until complete or partial resolution (Grade 0 to 1).

Resume Lutathera at 3.7 GBq (100 mCi) in patients with complete or partial resolution. If reduced dose does not result in Grade 2, 3 or 4 thrombocytopenia, administer Lutathera at 7.4 GBq (200 mCi) for next dose. |
|                  | Recurrent Grade 2, 3 or 4   | Permanently discontinue Lutathera.   |
| Anemia           | First occurrence of:
Grade 3 (Hgb < 8.0 g/dL); transfusion indicated
Grade 4 (life threatening consequences)  | Withhold dose until complete or partial resolution (Grade 0, 1, or 2).

Resume Lutathera at 3.7 GBq (100 mCi) in   |

| Adverse Reaction | Worst Toxicity CTCAE Grade (unless otherwise specified)  | Dose Modification  |
|------------------|--|--|
|                  |  | patients with complete or partial resolution. If reduced dose does not result in Grade 3 or 4 anemia, administer Lutathera at 7.4 GBq (200 mCi) for next dose.   |
|                  | Recurrent Grade 3 or 4   | Permanently discontinue Lutathera.   |
| Neutropenia      | First occurrence of:
Grade 3 (ANC < 1.0 - 0.5 x 10  /L)
Grade 4 (ANC < 0.5 x 10  /L)   | Withhold dose until complete or partial resolution (Grade 0, 1, or 2).

Resume Lutathera at 3.7 GBq (100 mCi) in patients with complete or partial resolution. If reduced dose does not result in Grade 3 or 4 neutropenia, administer Lutathera at 7.4 GBq (200 mCi) for next dose.       |
|                  | Recurrent Grade 3 or 4   | Permanently discontinue Lutathera.   |

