|                  | Defined as:
First occurrence of:

Creatinine clearance less than 60 mL/min; calculate using Cockcroft Gault with actual body weight, or

40% increase in baseline serum creatinine, or

40% decrease in baseline creatinine clearance; calculate using Cockcroft Gault with actual body weight. | Withhold dose until complete resolution.

Resume Lutathera at 3.7 GBq (100 mCi) in patients with complete resolution. If reduced dose does not result in renal toxicity, administer Lutathera at 7.4 GBq (200 mCi) for next dose.  |
| Renal Toxicity   | Recurrent renal toxicity as described above  | Permanently discontinue Lutathera.   |
|                  | Defined as:
First occurrence of:

• Bilirubinemia >3 times the upper limit of normal (Grade 3 or 4), or

• Hypoalbuminemia less than 30 g/L with a decreased prothrombin ratio less than 70%.

   | Withhold dose until complete or partial resolution (Grade 0, 1 or 2).

Resume Lutathera at 3.7 GBq (100 mCi) in patients with complete or partial resolution. If reduced Lutathera dose does not result in G3 or 4 bilirubinemia, administer Lutathera at 7.4 GBq (200 mCi) for next dose. |
|                  | Recurrent hepatotoxicity   | Permanently discontinue Lutathera.   |

| Adverse Reaction                                    | Worst Toxicity CTCAE Grade (unless otherwise specified) | Dose Modification   |
|---|---|---|
| Any other CTCAE* Grade 3 or Grade 4 AE  | First occurrence of:
Grade 3 or 4                    | Withhold dose until complete or partial resolution (Grade 0 to 2).

Resume Lutathera at 3.7 GBq (100 mCi) in patients with complete or partial resolution. If reduced dose does not result in Grade 3 or 4 toxicity, administer Lutathera at 7.4 GBq (200 mCi) for next dose. |
|   | Recurrent Grade 3 or 4                                  | Permanently discontinue Lutathera.  |

 No dose modification required for hematological toxicities Grade 3 or Grade 4 solely due to lymphopenia

\*CTCAE: Common Terminology Criteria for Adverse Events, National Cancer Institute

In addition,

- permanently discontinue treatment with Lutathera if hypersensitivity due to the active substance or any of the excipients of Lutathera is observed;
- temporarily discontinue treatment with Lutathera, until resolution or stabilisation before treatment can be resumed:

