## 2.6.4 Laboratory data

The routine laboratory tests are assessed locally at each investigational site. The summaries will include all on-treatment assessments available for the lab parameter collected no later than 56 days after the last study treatment administration date (see Section 2.1.1) as well as including all short-term and long-term assessments cumulatively in separate summaries.

The following summaries will be produced for hematology, biochemistry and urinalysis laboratory data as well as for safety biomarkers (by laboratory parameter):

- Worst on-treatment CTC grade (regardless of the baseline status). Each participant will be counted only for the worst grade observed on-treatment.
- Shift tables using CTC grades to compare baseline to the worst on-treatment value.
- For laboratory tests where CTC grades are not defined, shift tables using the low/normal/high/(low and high) classification to compare baseline to the worst on-treatment value.

These summaries will be repeated including the short-term and long-term follow-up periods, respectively.

The following listings will be produced for the laboratory data:

- Listings of all laboratory data, with CTC grades and classification relative to the laboratory normal range. Lab data collected during the short-term and long-term follow-up periods will be flagged.
- Listing of all CTC grade 3 or 4 laboratory toxicities

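### No SAP laboratory table counts the protocol's own renal toxicity criteria, so a patient who meets a 40%-from-baseline criterion can read as normal or high in the creatinine clearance table

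*SAP*

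**What the plan says.** Protocol Section 6.5.1.1, Table 6-4, sets out dose modifications under the column heading "Worst Toxicity CTCAE Grade (unless otherwise specified". For the kidney it does specify otherwise. Renal toxicity is the first occurrence of any of three findings:

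- "Creatinine clearance less than 60 mL/min", by Cockcroft-Gault with actual body weight
- "40% increase in baseline serum creatinine"
- "40% decrease in baseline creatinine clearance", by the same formula

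The stated consequence is "Withhold dose until complete resolution".

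The SAP tabulates laboratory data in a different way. Section 2.5.2 (Safety, first cycle) gives "Worst post-baseline CTC grade (regardless of the baseline status", a CTC-grade shift table, and a low/normal/high shift table for tests without CTC grades. Section 2.6.4 gives "Worst on-treatment CTC grade (regardless of the baseline status" with the same two shift tables, and repeats them with short-term and long-term follow-up included. Section 5.3 assigns grades by program from CTCAE version 5.0. For ungraded tests it uses laboratory normal ranges or project-specific ranges, which it does not state.

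The protocol's own analysis text points the same way. Section 12.5.2 (Clinical laboratory evaluations) prescribes low/normal/high shift tables, and Appendix 3 applies CTCAE to the severity of laboratory toxicities.

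**The concern.** The kidney is one of the two target organs for radiation toxicity, and laboratory toxicities after the first dose are part of a co-primary endpoint. The protocol has stated which renal change it regards as toxicity, and two of its three criteria are relative to the patient's own baseline. A table built on grades or population bands does not show who crossed such a line.

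The SAP does pre-specify thresholds or baseline-change categories elsewhere: liver enzymes and bilirubin (2.6.4), ECG intervals and heart rate (2.6.5.1), and weight, blood pressure and pulse (Table 2-1). It has none for renal function. At stake is whether the first-cycle and cumulative safety tables show, by a fixed rule, how many adolescents met the renal criteria that the protocol set.

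**Working it through.** The plan gives no figure on this point, so there is none to reproduce. The check applies the protocol's formula to the three criteria and asks which band each result falls in.

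**Inputs**

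- Formula (Protocol Table 8-4): CrCl = (140 − age) × weight / (72 × creatinine in mg/dL), × 0.85 for females.
- Entry criterion (Protocol Section 5.2): CrCl below 70 mL/min is excluded.
- Band (Protocol Section 4.2): adolescent reference limits of about 70 to 108 mL/min. Using these as the low and high limits of the CrCl table is an assumption; the SAP does not state the limits.
- Age and weight held constant over the comparison; 40% read as at least 40%.

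**How the two 40% criteria relate**

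- Creatinine +40%: CrCl is multiplied by 1/1.4 = 0.714, a fall of 28.6%.
- CrCl −40%: creatinine is multiplied by 1/0.6 = 1.667, a rise of 66.7%.

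**Where a patient who just meets each criterion lands**

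The cut-points are 70 × 1.4 = 98, 108 × 1.4 = 151.2, 70 / 0.6 = 116.7 and 108 / 0.6 = 180.

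| Criterion | Baseline CrCl (mL/min) | CrCl when just met | Entry in band table |
|---|---|---|---|
| Creatinine +40% | 70 to under 98 | 50 to under 70 | low |
| | 98 to 108 | 70 to 77.1 | normal to normal |
| | above 108 to 151.2 | 77.1 to 108 | high to normal |
| | above 151.2 | above 108 | high to high |
| CrCl −40% | 70 to under 116.7 | 42 to under 70 | low |
| | 116.7 to 180 | 70 to 108 | high to normal |
| | above 180 | above 108 | high to high |
| CrCl under 60 | any | under 60 | low |

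**Worked cases**

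- Girl, 12 years, 40 kg, creatinine 0.60 to 0.84 mg/dL (0.84 / 0.60 = 1.40). Before: 128 × 40 × 0.85 / (72 × 0.60) = 100.7. After: 128 × 40 × 0.85 / (72 × 0.84) = 72.0. The creatinine criterion is met; the CrCl table reads normal to normal.
- Boy, 15 years, 55 kg, creatinine 0.60 mg/dL. Before: 125 × 55 / (72 × 0.60) = 159.1. A 40% fall gives 95.5, at creatinine 0.60 / 0.6 = 1.00. The CrCl criterion is met; the table reads high to normal.

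**Serum creatinine itself.** The documents give no upper limit of normal (ULN) and do not reproduce the CTCAE criteria. A 40% rise stays at or below the ULN when baseline is at most ULN / 1.4. With an assumed ULN of 0.7, 1.0 or 1.2 mg/dL, that is a baseline of up to 0.50, 0.71 or 0.86. The girl's 0.84 is within normal if the ULN is at least 0.84. Whether such a rise also receives a CTC grade relative to baseline cannot be settled from the documents.

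**Other places where the patient might be seen**

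- Adverse events: under Protocol 10.1.1 an abnormal value is an event only if it causes symptoms, is judged clinically significant or needs therapy.
- Nephrotoxicity as an adverse event of special interest (AESI; Protocol 10.1.5): the wording covers markedly reduced clearance but gives no 60 mL/min or 40% cut-off. The first-cycle output list in SAP 2.5.2 has no AESI table.
- Dose interruptions with reasons (SAP 2.4.1): counted only if a later dose was changed, which cannot happen after dose 4.
- Follow-up: Protocol 8.4.1 records only related serious events and AESIs, plus all secondary malignancies, and the SAP lists these events without summarising them.
- Listings: all laboratory values are listed (SAP 2.6.4).

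**The case against.** The strongest reply is that Table 6-4 is a dose-modification rule, not an endpoint definition. Protocol Section 12.4.1 sends first-cycle laboratory toxicities to Section 12.5.2, which asks for low/normal/high shifts, and Appendix 3 names CTCAE. The SAP follows both. This stands: a reader might infer that the SAP contradicts the protocol, and it does not.

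A reader might also infer that a patient whose dose is withheld for renal toxicity would be reported as normal throughout. The documents do not support that. A withheld dose is counted, with its reason, under SAP 2.4.1. A reported event enters the first-cycle event tables (2.5.2), the table of events leading to interruption (2.6.1) and, where applicable, the on-treatment AESI summary (2.6.1.1). The on-treatment period runs to 56 days after the last dose, so the event and AESI summaries do cover the weeks after dose 4. What remains is that the event routes rest on investigator judgement and the interruption route needs a later dose.

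Nor does the problem extend to all three criteria. CrCl below 60 reads as low on the cited limits. To say that all three lie outside CTC grading would need CTCAE text that the documents do not contain.

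Finally, with about 8 to 11 patients and every value listed, a reader could work out the counts by hand. That limits the harm but does not supply a pre-specified count.

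**Conclusion.** The point holds as an omission. No SAP laboratory table counts the Table 6-4 renal criteria, and the two 40% criteria can be met while CrCl stays within or above the normal band. For the creatinine criterion this needs a baseline CrCl of at least 98 mL/min; for the CrCl criterion, at least 116.7. It concerns the laboratory tables only and does not show that renal toxicity would go unreported overall.

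The number of patients affected cannot be estimated from the documents. One patient is 1/8 = 12.5% at the minimum sample size, or 1/11 = 9.1% of the 11 enrolled when Amendment 03 was written; that is the weight of a single case, not an expected error.

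The conclusion assumes that the 70-108 limits serve as the CrCl band and that weight is constant over the comparison. It makes no claim about how serum creatinine would be graded.

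**What to change.** In SAP 2.5.2 (first cycle) and 2.6.4 (on-treatment, and to 6 months after the last dose), add the number and percentage of patients meeting each of the three Table 6-4 renal criteria, and any of them. Derive these by program from baseline and from all scheduled and unscheduled values, and add a listing of the qualifying values.

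For long-term follow-up, give the listing only, or interpret the counts with caution, because age and weight enter Cockcroft-Gault. As an illustration with assumed growth, the girl above at 15 years and 50 kg with creatinine still 0.60 has CrCl 125 × 50 × 0.85 / (72 × 0.60) = 123.0. That is 22% above her baseline of 100.7 with no change in creatinine.

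The cost is SAP wording, one descriptive table and one listing. Creatinine and CrCl are already collected, and Protocol 8.4.4 has weight measured for each CrCl calculation. The downside is that some flagged values may not be clinically important. No dosing rule changes.
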